3.1.1.1 Inclusion and Exclusion Criteria

To participate in each cross-sectional surveys (baseline and post vaccination), one child per household will be randomly selected for the nasopharyngeal sampling if he is eligible for enrolment after meeting the following inclusion criteria:

- Aged 1-9 years
- Residing in the villages included in the study
- Parent or caretaker provides informed consent for the child to participate in the study

Exclusion criteria for participating in the surveys will include the following:

- Head or facial injuries that contraindicate nasopharyngeal swabbing
- Any condition or criteria, including acute or chronic clinically significant abnormality that in the opinion of the investigator might compromise the wellbeing of the participant or interfere with the outcome of the study

For mass vaccination campaigns, all children of the target age group for vaccination, for instance aged 1-9 years of age, residing in the study villages allocated to full or fractional dose arm will be targeted for vaccination.

Children meeting the following inclusion criteria will be eligible for vaccination:

- Aged 1-9 years
- Residing in the villages included in the study and allocated to vaccination
- Head of the household or main caretaker provides consent for the child to be vaccinated

Exclusion criteria for vaccination will include the following:

- Hypersensitivity to any component of the vaccine, including diphtheria toxoid
- Vaccination with a PCV vaccine within the previous 4 weeks, as there should be a minimum of 4 weeks between doses
- Moderate or severe febrile illness (temperature $\geq 39^{\circ}\text{C}$) is a temporal contraindication, and the child should not be vaccinated until improvement.
- Any condition or criteria, including acute or chronic clinically significant abnormality that in the opinion of the clinical staff might compromise the wellbeing of the volunteer

3.1.1.2 Withdrawal/Discontinuation Criteria

In accordance with the principles of the Declaration of Helsinki a participant has the right to withdraw from any part of the study at any time and for any reason and is not obliged to give their reasons for doing so.

The mass vaccination consists of a single dose while outcomes are at the community level measured through two cross-sectional surveys. However, individual participants (in surveys or the qualitative study) may withdraw their consent and in that case their data will not be included in the data analysis.

3.1.2 Sample Size and Power Considerations

The sample size has been calculated to respond to the objective of determining whether community level prevalence of VT pneumococci after a fractional dose PCV mass campaign among children aged 1-9 years is non-

Determining whether mass campaigns with fractional dose PCV10 would accelerate herd protection against pneumococcal transmission in Sub-Saharan Africa

inferior to that seen after a mass campaign among children aged 1-9 years using full dose PCV as well as determining the superiority of a full dose PCV mass campaign compared to no vaccination. Based on NP carriage studies conducted in Sub-Saharan Africa settings and considering an estimated coverage of 3 doses of PCV in children < 12 months of age of 48% in the study area, we estimate the prevalence of VT carriage, among 1-9 year old, to be between 25 and 35% and take the middle value, 30%, as an initial estimate. We assume a 50% reduction in PCV10 VT carriage after vaccination with a full dose and consider the prevalence of VT carriage amongst vaccinated children with a full dose 6 months after the vaccination campaign to be 15%.

Based on information from a study conducted in the area, we consider an intra-cluster correlation coefficient of 0.02. To test the non-inferiority of a mass campaign using fractional doses compared to a mass campaign using full doses, we have chosen a non-inferiority margin of 7.5% to ensure that a campaign with fractional doses provide at least half of the benefits provided by a campaign using full doses. We consider a 2.5% level of significance for a one-sided test and 90% power. With these assumptions, 27 clusters with 36 households sampled per cluster would provide a power of at least 90% (1944 individuals, with 972 in the full dose and 972 in the fractional dose arm). Non-inferiority will be achieved if the lower limit of the 95% confidence interval (CI) around the difference in the proportion of children with VT carriage (full dose group – fractional dose group) is $> -7.5\%$.

Given the sample size of the full-dose arm to test non-inferiority as described above, to test the superiority of a mass campaign to the control (non-vaccinated) arm, and considering a 5% level of significance for a two-sided test and 90%, we would need to sample 9 clusters with 30 households apiece in both the full-dose and control arms. Since the non-inferiority evaluation requires a larger sample size, the control arm will include the larger number of participants per cluster, which will lead to >90% power to detect superiority.

For the NP carriage survey, one participant will be sampled from each household. We consider that most households will have a child aged 1 to 9 years of age, but account for 20% refusal to participate and/or absences and increase the number of households to be invited to participate by 20%. All selected households having a child of the target age group will be invited to participate in the social contacts survey. Table 1 summarizes the number of cluster and households to be included in each survey.

Table 1. Initial estimates of clusters and households to be invited to participate in each survey

Allocation	Nº clusters	Nº households	Total participants
Control arm	9	36	324
Full dose arm	27	36	972
Fractional dose arm	27	36	972
Total	63	108	2268

The baseline prevalence of VT carriage is expected to be between 25 and 35% as described below. In case the results from the baseline survey differ significantly, the sample size may be re-evaluated. Once baseline survey results are available, they will be presented to TSC with simulation on power calculations outlining various

scenarios for the follow-up survey. Sample size may be re-estimated and the number of children may be increased following this review.

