6.1 Definition of outcomes

Effect of PCV10 campaign

The effect of a single dose PCV10 campaign in the reduction of VT carriage will be assessed by: first, assessing the superiority of a campaign using full doses of PCV10 compared to control group without vaccination; and second, by establishing the non-inferiority of a campaign using fractional doses of PCV10 compared to a campaign using full doses.

NP carriage will be measured in the 3 study arms (full dose arm, fractional dose arm and control arm) in a baseline survey implemented prior to the vaccination campaign and in a post-vaccination survey conducted 6 months post-vaccination campaign.

The NP carriage of VT *S. pneumoniae* will be measured as the proportion of participants that are colonized with any of the 10 serotypes covered by PCV10 at each time point. The reduction in NP carriage will be calculated by comparing the proportion of children carrying VT pneumococci 6 months post-vaccination to baseline, at the time of vaccination. Prevalence of colonization of non-VT serotypes will also be described at both timepoints.

Vaccine safety

Vaccine safety will be monitored up to 28 days after vaccination and all AEs and SAEs will be recorded.

Cost-effectiveness and modelling study

An age-structured, dynamic, deterministic model of pneumococcal transmission will be constructed to estimate the impact of mass fractional dose PCV campaigns on VT carriage. The model will use the

data on social interactions between age groups and PCV coverage estimates collected during the baseline survey as well as the results of the VT carriage from the baseline survey.

Based on the modelled epidemiological impact of PCV10 mass campaigns, with both full and fractional doses, a cost-effectiveness analysis will be performed to estimate the incremental cost-effectiveness ratio of routine PCV10 mass campaigns.

The modelled epidemiological impact and cost-effectiveness of a fractional dose mass campaign will be used to inform ongoing discussions of dose-sparing strategies and the use of single-dose fractional PCV in acute humanitarian emergencies.

Facilitators and barriers to implementing mass campaigns of fractional dose PCV

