7.5.1 Inclusion and exclusion criteria

Households containing at least one member aged 1-9 years whose head of the household or main caretaker provides consent to participate will be eligible to participate.

To participate in the carriage surveys, children meeting the following inclusion criteria are eligible for enrolment:

- (4) Aged 1-9 years
- (5) Residing in the villages included in the study
- (6) Parent or caretaker provides informed consent for the child to participate in the study

Exclusion criteria for participating in the carriage survey will include the following:

- (3) Head or facial injuries that contraindicate nasopharyngeal swabbing
- (4) Any condition or criteria, including acute or chronic clinically significant abnormality that in the opinion of the investigator might compromise the wellbeing of the participant or interfere with the outcome of the study

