7.5.2 Screening procedures and enrolment

The baseline and 6-months post-vaccination surveys will follow similar screening and enrolment procedures. Survey teams will visit randomly selected households and will go through the informed consent process with the head of the household (see sections 7.4 and 9.9).

In the pre-vaccination survey we will:

- 1) Administer a household questionnaire to the head of the household to collect information on the number of members who live in the household, their age and sex, school or other day care attendance of the children living in the household, PCV vaccination status of children living in the household, exposure to solid fuel smoke, and smoking habits.
- 2) Select a household member at random (using a simple lottery system) to collect information on the number of contacts with people of different age groups in the last 24h. This information will be collected using the social interactions questionnaire. If this person is absent from the household, a second attempt at a pre-scheduled time will be arranged. If the person is still unreachable after a second attempt the social contact questionnaire will not be completed.

3) Select a child aged 1 to 9 years of age at random (using a simple lottery system) for nasopharyngeal sampling. A short questionnaire will be used to collect the child's recent symptoms of an upper respiratory tract infection, including receiving any antimicrobials in the previous two weeks. If the selected child is temporarily absent from the household, a second attempt of inclusion will be made at another agreed upon time. In the rare event that the child is not eligible to participate another member will be randomly selected from the list. In the unlikely event that no child in the household is eligible to participate in the survey, the household will not be replaced.

In the post-vaccination survey we will:

- 1) Administer a household questionnaire to the head of the household to collect information on the number of members who live in the household, their age and sex, school or other day care attendance of the children living in the household, PCV vaccination status of children living in the household in the EPI, exposure to solid fuel smoke, smoking habits, and PCV vaccination during the study campaign from all children of the target age group.

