For the NP carriage survey, one participant will be sampled from each household. We consider that most households will have a child aged 1 to 9 years of age, but account for 20% refusal to participate and/or absences and increase the number of households to be invited to participate by 20%. All selected households, even if they do not have a child of the target age group, will be invited to participate in the social contacts survey. Table 1 summarizes the number of cluster and households to be included in each survey.

Table 1. Initial estimates of clusters and households to be invited to participate in each survey

Allocation	Nº clusters	Nº households	Total participants
Control arm	9	36	324
Full dose arm*	27	36	972
Fractional dose arm	27	36	972
Total	63	108	2268

*Adjustment for multiplicity will be done at the analysis phase if necessary

In order to adjust the initial estimates, sample size will be recalculated with VT carriage data obtained from the baseline survey.

The sample size calculations were performed using PASS 14 (Power Analysis and Sample Size Software (2015). NCSS, LLC. Kaysville, Utah, USA).

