2.2 Secondary Objectives

Analysis of the following secondary objectives will be described in this SAP:

- To measure the age-stratified prevalence of NP carriage of *S. pneumoniae* in children 1-9 years of age in the study area.

- To determine the effect of a mass vaccination campaign with one full dose of PCV in children 1 to 9 years of age on VT pneumococci carriage 6 months after vaccination
- To assess the occurrence of adverse events (AE) during 7 days and serious adverse events (SAE) during 28 days after administration of fractional and full doses of PCV.

The analyses of the two following secondary objectives will be described elsewhere:

- To model the potential effect of fractional dose PCV campaigns in other contexts using the results of the clinical trial.
- In the setting of a qualitative study, to develop recommendations on how a potential future fractional dose PCV mass campaign could be successfully planned, communicated, delivered and integrated into national immunization programmes using qualitative analysis.

3. Study Design and Assessment

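### Protocol and SAP give opposite rules on whether households without a child aged 1-9 join the baseline social-contact survey, which feeds the transmission model

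*Combined protocol and SAP*

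**What the plan says.** Three places set a rule for which households enter the social-contact survey.

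- Protocol 7.12, on the social-contact survey: "All selected households, even if they do not have a child of the target age group, will be invited to participate".
- SAP 3.1.2, in the otherwise matching paragraph: "All selected households having a child of the target age group will be invited to participate in the social contacts survey".
- Protocol 7.5.1, on taking part in the cross-sectional surveys in general: "Households containing at least one member aged 1-9 years whose head of the household or main caretaker provides consent to participate will be eligible". It makes no exception for the contact questionnaire.

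The respondent need not be a child. Protocol 7.5.2, for the pre-vaccination survey and contacts across age groups, says: "Select a household member at random (using a simple lottery system) to collect information on the number of contacts". Households are drawn by simple random sampling from a complete listing of household heads in the cluster (protocol 7.1, SAP 3.1.1), so the frame is not limited to homes with children.

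Protocol 6.1 gives the use of the data: the age-structured transmission model will draw on "data on social interactions between age groups and PCV coverage estimates collected during the baseline survey", and a cost-effectiveness analysis rests on the modelled impact. For the modelling objective and the qualitative objective, SAP 2.2 states: "The analyses of the two following secondary objectives will be described elsewhere".

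**The concern.** A child aged 1-9 is needed for the nasopharyngeal swab. Nothing in either document says why a contact respondent must live with one. Protocol 7.12 plainly considered households without such a child and included them; the SAP reverses this without comment.

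At stake is whom the contact data describe. Under the narrower rule, adolescents, adults and older people who live without young children are never interviewed. They can be expected to meet fewer 1-9 year olds than people of the same age who live with them. The contact rates of the older age groups with the vaccinated ages would then come from a selected part of the population, and would probably be too high. Because the documents differ, practice could also vary between teams or clusters unless one rule is fixed.

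**Working it through.** **1. The plan's own figures, and whether they depend on the rule.** The plan gives no sample size for the contact survey. The figures in the same section concern carriage.

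Non-inferiority inputs (protocol 7.12, SAP 3.1.2): 15% carriage in both vaccine arms, margin 7.5 points, one-sided 2.5%, power 90%, intra-cluster correlation 0.02, 27 clusters of 36 per arm.

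- Before clustering: n = (1.960 + 1.282)² × 2 × 0.15 × 0.85 / 0.075² = 10.51 × 0.255 / 0.005625 = 476.5, so 477 per arm.
- Design effect: 1 + 35 × 0.02 = 1.70. Effective n per arm: 972 / 1.70 = 571.8.
- SE = √(0.255 / 571.8) = 0.0211. Power = Φ(0.075 / 0.0211 − 1.960) = 94.4%, consistent with the stated minimum of 90%.

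Superiority, 30% against 15%, with 9 control and 27 full-dose clusters of 36: effective n is 324 / 1.70 = 190.6 and 571.8. The SE is 0.0326 pooled under the null and 0.0364 unpooled. Power = Φ((0.15 − 1.960 × 0.0326) / 0.0364) = 99.1%, consistent with the stated figure of more than 90%.

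The swab requires a child aged 1-9 under either wording, so neither result moves with the contact-survey rule.

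**2. The passages side by side, for a drawn household with no member aged 1-9.**

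| Passage | Contact survey | Swab |
|---|---|---|
| Protocol 7.12 | invited | not possible |
| SAP 3.1.2 | not among those invited | not possible |
| Protocol 7.5.1 | household not eligible | not possible |

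**3. Who is lost.** Every child aged 1-9 lives in a household that meets the narrower rule, so contacts reported by children of that age are untouched. The loss falls on respondents aged 10 and over.

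**4. Possible size.** Let f be the share of the contact sample living in households without a child aged 1-9. Let r be their mean contacts with 1-9 year olds relative to respondents in other households. Leaving them out overstates the mean by 1 / [(1 − f) + f × r] − 1. Neither f nor r is in the documents, which say only that most households are thought to have such a child. Both ranges below are assumptions.

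| f | Households of 2268 | r = 0.25 | r = 0.50 | r = 0.75 | r = 1 |
|---|---|---|---|---|---|
| 5% | 113 | 3.9% | 2.6% | 1.3% | 0 |
| 10% | 227 | 8.1% | 5.3% | 2.6% | 0 |
| 20% | 454 | 17.6% | 11.1% | 5.3% | 0 |
| 30% | 680 | 29.0% | 17.6% | 8.1% | 0 |

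For example, f = 10% and r = 0.50 gives 1 / (0.90 + 0.05) − 1 = 5.3%. The household counts are f × 2268 and take all drawn households as the contact sample.

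**The case against.** **The restriction rests on thin text.** SAP 3.1.2 does not use the word only, and its sentence sits in a sample-size section. SAP 3.1.4 and 3.2.3, which describe data collection, set no child condition for the contact respondent. Within the protocol, 7.12 can be read as a specific exception to the general rule in 7.5.1, and field teams work from the protocol. This weakens any claim that teams are bound to receive conflicting orders. It does not remove the conflict: the natural reading of the SAP sentence is restrictive, and 7.5.1 carries no exception.

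**Bias is not shown.** A reader might infer that the SAP rule demonstrably biases the model, and with it the herd effect and the cost-effectiveness result. The documents do not support that. The modelling plan lies outside this SAP, so any weighting is out of view; f and r are unknown; zero is possible; and no step in the documents links a shift in contact rates to either output. This objection stands. It has one limit: no later weighting can recover the contacts of households that were never interviewed.

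**Inviting every household does not by itself make the sample representative.** One member is interviewed per household, so people in large households are less likely to be chosen under either rule. If households without young children are smaller, an unweighted sample would over-represent their members. This stands and belongs in the fix.

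**The change is more than wording.** One consent form (protocol 7.4, second in the list) covers both survey participation and swabbing of a child, and a change to 7.5.1 may need review under protocol 9.7.3 and 10.1. This also stands.

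**Conclusion.** The inconsistency is established from the text: protocol 7.12 on one side, SAP 3.1.2 and protocol 7.5.1 on the other, with no explanation. The expected consequence of the narrower rule is a contact sample without people aged 10 and over who live apart from young children, and probably an overstatement of contacts with 1-9 year olds at those ages. Its size is unknown. The range of about 1% to 29% holds only for the assumed f of 5-30% and r of 0.25-0.75, and the effect vanishes at r = 1. No cell of that table should be quoted as an estimate for this trial.

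The reach is limited to the secondary modelling objective and the cost-effectiveness work built on it. A reader might extend the concern to the primary result; the carriage comparison, its sample size and its power are the same under either rule.

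**What to change.** State one eligibility rule for the contact survey in protocol 7.5.1, protocol 7.12 and SAP 3.1.2. The rule in 7.12 is preferable because it matches the sampling frame, the respondent of any age and the purpose of the data:

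- every drawn household is eligible for the household and social-contact questionnaires at baseline;
- having a member aged 1-9 is a condition for the swab component only;
- the number of drawn households without such a member is recorded and reported;
- contact data are weighted by household size, which the household questionnaire already collects, because one member per household is interviewed.

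If the restriction was intended, or the baseline survey has already applied it, say so with the reason, report how many households were excluded, and note the limitation for the model.

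Cost: a short questionnaire in the households without young children, which are already drawn, so no further households are needed. The sponsor should also check that the survey consent form suits a household with no child to swab, and whether the change to 7.5.1 requires a protocol amendment.

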3.1.3 Randomization and Blinding

Following the results of the baseline survey, clusters will be randomized in a 3:3:1 ratio, with 27 clusters randomized to receive a campaign with the full dose, 27 clusters randomized to receive a campaign with the fractional dose and 9 clusters randomized to the control arm. Randomization will be stratified by proximity to nearest health center (<5 km vs ≥5 km). In the event of significant imbalance in carriage of VT pneumococci between clusters in the baseline survey, randomization will also be stratified by baseline prevalence, after a decision by the trial steering committee. An equal or proportional number of clusters will be randomized to each study arm from each stratum. The study statistician randomization will prepare the material to generate the list (blocked randomization with fixed block size if only one stratum, by minimisation if more than one stratum), and the final list will be generated by an independent statistician who has no contact with study participants. Study implementation will be blinded to the extent possible. Vaccination nurses will not be blinded to the vaccine they are giving, but they will not communicate vaccine allocation to other members of the team or to participating villages. Villages randomized to the control arm will not receive any “dummy” intervention, so will not be blinded to their group allocation. The trial will be observer-blind in that personnel at KWTRP will be blinded to group allocation until after the completion of culture and serotyping in each survey.

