7.11 Randomization and blinding procedures

Following the results of the baseline survey, clusters will be randomized in a 3:3:1 ratio, with 27 clusters randomized to receive a campaign with the full dose, 27 clusters randomized to receive a campaign with the fractional dose and 9 clusters randomized to the control arm. Randomization will be stratified by proximity to nearest health center (<5 km vs. ≥5km). In the event of significant imbalance in carriage of VT pneumococci between clusters in the baseline survey, randomization will also be stratified by baseline prevalence. An equal or proportional number of clusters will be randomized to each study arm from each stratum.

The randomization list will be generated by an independent statistician with no other contact with trial participants.

Study implementation will be blinded to the extent possible. Vaccination nurses will not be blinded to the vaccine they are giving, but they will not communicate vaccine allocation to other members of the team or to participating villages. Villages randomized to the control arm will not receive any “dummy” intervention, so will not be blinded to their group allocation. The trial will be observer-blind in that personnel at KWTRP will be blinded to group allocation until after the completion of culture and serotyping in each survey.

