3.1.1 Study cohorts

Clusters will be randomized to full dose mass vaccination campaigns, fractional dose mass vaccination campaigns or the control arm in 3:3:1 allocation ratio. Clusters will be composed of a village or group of closely-neighbouring villages that share a school or market, and will be limited to a population of between 500 and 4000 persons. Stratified randomization will be used to account for proximity to the nearest health centre (<5 km vs ≥5 km). In the event of significant imbalance in carriage of VT pneumococci between clusters in the baseline survey, randomization may also be stratified by baseline prevalence upon the decision of the Trial Steering Committee. For this reason, randomization will happen after the results of the baseline survey are known.

Vaccination will target all children aged 1 to 9 years of age residing in the selected villages. (If baseline survey data unexpectedly shows very low prevalence of carriage at the extremes of this age range, the target age group may be adjusted upon recommendation of the trial steering committee.) We estimate that children eligible for the vaccination campaigns will represent 30% of the total population. With an estimated average of 2000 people per cluster, vaccination will target approximately 600 children 1-9 years of age in each cluster receiving vaccine. In total, in the 54 clusters receiving vaccine, the mass vaccination campaign with single full- or fractional-dose PCV is expected to target approximately 32,400 children 1-9 years of age.

Prior to the mass vaccination campaign, a cross-sectional survey will be implemented to estimate community-level carriage of VT pneumococci, as well as to collect data on household composition, social interactions and PCV vaccination coverage in the routine EPI. A total of 36 households in each cluster will be invited to participate in the cross-sectional survey. For the purposes of this study, a household is defined as a group of people living under the authority of a head of household, sleeping under the same roof, and sharing at least one meal per day, for at least two weeks, independent of any family ties. Selection of households will be based on probability sampling. The required number of households in each cluster will be randomly selected using simple random sampling based on an exhaustive list of heads of household in the cluster.

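### Balancing on baseline VT carriage hangs on an undefined trigger, and minimisation is not reconciled with fixed 27:27:9 totals; one constrained allocation of all 63 clusters would settle both cheaply

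*Combined protocol and SAP*

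**What the plan says.** Allocation waits for the baseline survey. SAP 3.1.1 gives possible stratification by carriage as the reason: "For this reason, randomization will happen after the results of the baseline survey are known". Proximity to a health centre (two levels) is always a stratification factor. Baseline prevalence is conditional, and four places describe the condition differently:

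- Protocol 7.1 and 7.11: if clusters show significant imbalance, "randomization will also be stratified by baseline prevalence. An equal or proportional number of clusters will be randomized to each study arm from each stratum" (wording of 7.11). No committee step is mentioned.
- SAP 3.1.1: "randomization may also be stratified by baseline prevalence upon the decision of the Trial Steering Committee".
- SAP 3.1.3: the condition is "In the event of significant imbalance in carriage of VT pneumococci between clusters in the baseline survey"; stratification then follows, after a steering committee decision.

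None of them gives a test, a threshold, a cut-point or a number of prevalence strata.

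On totals, SAP 3.1.3 says "clusters will be randomized in a 3:3:1 ratio, with 27 clusters randomized to receive a campaign with the full dose", the same number for the fractional dose, and "9 clusters randomized to the control arm". It adds: "An equal or proportional number of clusters will be randomized to each study arm from each stratum". The method is "blocked randomization with fixed block size if only one stratum, by minimisation if more than one stratum". No unequal-ratio rule, random element or constraint on the totals is stated for the minimisation.

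SAP 4.1 defines the primary endpoint as change from baseline, and SAP 3.1.1 makes the two surveys independent samples. SAP 4.3.2.1 plans adjusted analyses that include baseline VT prevalence and the stratification factor. SAP 4.3 tests non-inferiority only if full dose beats control.

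**The concern.** There are two separate defects.

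First, imbalance is a property of arms, and there are no arms when the condition is applied. Differences between clusters reflect the ICC plus sampling error. Two statisticians with the same baseline data could decide differently, and the word *may* in one place against *will* in the others leaves open whether a decision is needed at all. Yet the case for balancing 9 control clusters against 27 on the baseline value of the outcome does not depend on a test, and the data for it are in hand by design. What is at stake is precision in the control comparison, which is also the gate to the non-inferiority test.

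Second, the stated totals and the proportional split within strata are hard constraints, while standard minimisation treats balance as a target. Minimisation applies at least whenever prevalence is added. Read literally it always applies, because proximity alone makes two strata. The section does not say how the two are made compatible.

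**Working it through.** **Inputs from the documents (SAP 3.1.2, 3.1.3; protocol 7.12).** 27/27/9 clusters, m = 36 per cluster, ICC 0.02, VT prevalence 30% without vaccine and 15% after full dose, non-inferiority margin 7.5 points.
**Assumed.** Between-survey correlation of true cluster prevalence 0.8; the minimisation settings in step 5; a 5% chi-square test as one possible reading of the trigger.

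**1. The plan's own power.** Design effect 1 + 35 × 0.02 = 1.70 (1.58 at m = 30).
- Non-inferiority: SE = √(2 × 0.1275 × 1.70/972) = 2.11 points; 7.5/2.11 − 1.96 = 1.59, power 94.4%. The stated figure of at least 90% is reproduced.
- Superiority (pooled-null two-proportion formula): 91.7% for 9 v 9 clusters of 30, as stated; 99.1% for 9 v 27 clusters of 36.

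**2. Baseline difference, control v full, totals fixed, prevalence not balanced.** Here 1/9 + 1/27 = 0.1481.
- Variance of an observed cluster prevalence: 0.21 × 1.70/36 = 0.00992. SD of the observed difference = √(0.00992 × 0.1481) = 3.8 points; chance of exceeding 5 points about 19%.
- Between-cluster variance: 0.02 × 0.21 = 0.0042. SD of the true difference = √(0.0042 × 0.1481) = 2.5 points.
- Sampling error is therefore 1 − 0.0042/0.00992 = 58% of the observed variance.

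**3. Unadjusted change-from-baseline contrast.**
- Follow-up variance: 0.00992/9 + (0.1275 × 1.70/36)/27 = 0.00110 + 0.00022 = 0.00132 (SD 3.6 points).
- Covariance with baseline: 0.8 × 0.0042/9 + 0.8 × √(0.0042 × 0.00255)/27 = 0.00037 + 0.00010 = 0.00047.
- Not balanced: 0.00147 + 0.00132 − 2 × 0.00047 = 0.00185, SD 4.3 points.
- Balanced: the follow-up variance left after regression on observed baseline is 0.00878/9 + 0.00533/27 = 0.00117 (SD 3.4). Adding the small remaining baseline difference gives about 3.5, which simulation with nine prevalence-ordered blocks of seven also gives.
- Normal-approximation power for 15 points: 15/4.3 − 1.96 = 1.53 (94%) against 15/3.5 − 1.96 = 2.33 (99%).

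**4. Trigger.** For 63 beta-binomial clusters of 36, a 5% chi-square test of homogeneity rejects in about 91% of simulated surveys at ICC 0.02, 53% at 0.01 and 24% at 0.005. Under that reading, whether the design balances depends mainly on the ICC.

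**5. Minimisation at 3:3:1** on proximity and prevalence halves, half the clusters in each proximity level (800 runs per setting):

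| Assignment probability | Exactly 27:27:9 | Control arm, 95% range |
|---|---|---|
| 1.0 (deterministic) | 77% | 8–9 |
| 0.9 | 50% | 8–11 |
| 0.8 | 25% | 8–13 |

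A second simulation gave about 74% and 50% for the first two rows. The SD of the observed control-minus-full baseline difference was about 2.4 points, against 3.8 without balancing on prevalence.

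**The case against.** The case against is substantial, and much of it stands.

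- The trigger is less harmful than it looks. Between-cluster variation limits how large an arm imbalance can be, and at the planned ICC a 5% test would usually fire. In simulated trials where it did not, the true control-minus-full difference had SD 1.3, 1.7 and 2.3 points at ICC 0.005, 0.01 and 0.02. A true imbalance above 5 points occurred in at most about 3% of them. This stands, but the 5% test is itself an assumption; the documents name none. A committee decision supplies an authority and no criterion.
- The 3.8 points are mostly baseline sampling noise, which does not carry into an independent follow-up sample. The true SD of 2.5 falls only to about 2.0 with balancing, and the SD of the plain 6-month contrast only from 3.6 to 3.4. This stands for the 6-month contrast. It does not dispose of the point, because SAP 4.1 makes change from baseline the endpoint, and there the baseline noise enters directly.
- Adjustment for observed baseline prevalence would recover most of the gain; the 3.4 in step 3 is in effect an adjusted SD. But SAP 4.3.2.1 lists adjusted analyses without making them primary.
- More than one stratum may mean more than one factor, so that proximity alone leads to blocks. That is a fair reading and gives both branches a use. Minimisation still applies once prevalence is added.

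A reader might infer that minimisation causes imbalance in the control arm, or that no totals were set. Neither is supported: minimisation on prevalence reduces imbalance, and 27, 27 and 9 are stated in both documents. The defect is that the method and the totals are not reconciled.

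**Conclusion.** The point holds as a cheap improvement. The trigger cannot be applied as written and is described inconsistently. Not acting on it costs about 0.8 points of SD in the unadjusted control-minus-full change contrast (4.3 against 3.5), at ICC 0.02 and an assumed between-survey correlation of 0.8. The allocation method, as described, does not by itself deliver the stated totals, though simulated departures are usually small, never put the control arm below 8 clusters, and depend on assumed settings.

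A reader might conclude that the superiority test, and so the whole trial, is endangered. The plan's figures do not support that: power is 99.1% for the 6-month comparison and about 94% even for the unbalanced change contrast. Nor should the change-score result be carried over to non-inferiority. The corresponding full-minus-fractional SDs are about 2.8 and 2.0 to 2.2 points, but SAP 4.3.2.1 states that decision rule on the difference in proportions, with no baseline term.

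**What to change.** - Delete the conditional trigger in protocol 7.1 and 7.11 and SAP 3.1.1 and 3.1.3, and state that allocation always balances on cluster baseline VT prevalence and proximity.
- Replace blocks-or-minimisation by one allocation of all 63 clusters with totals fixed at 27:27:9, using covariate-constrained randomisation on both factors and a pre-stated constraint. As a guide, requiring all three observed arm means to lie within 2 points of each other accepted about 17% of random allocations at ICC 0.02 (prevalence only), and the totals hold by construction.
- If blocks of seven within proximity are preferred, add a rule for incomplete blocks. With proximity splits of 30/33, 31/32 or 24/39 and a truncated last block, simulated allocations were exactly 27:27:9 in only 22 to 27% of runs.
- Name both factors in the primary GEE model, and not only in the adjusted analyses.

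The cost is a rewritten randomisation paragraph and script, and the obligation to keep both factors in the primary model. No extra data or fieldwork is needed, because the baseline survey and the delayed randomisation are already planned.
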